The primary process outcomes are the number and proportion of smokers that can be recruited for further follow-up, including those who will not participate in the RCT but agree to enroll in the SC clinics. We hypothesize that the promotion sessions providing NRT sampling will recruit more smokers, and greater proportion of recruited smokers among those who will be approached than those sessions without NRT sample. Other secondary process outcomes include (1) total number of smokers who can be approached in outdoor urban places; and (2) number of smokers who accept the brief SC advice. All these indicators will be documented by the SCAs in the promotion sessions.

Phase 3: Quitting outcomes

The evaluation aims to assess the effectiveness of NRT sampling on using the SC services and quit attempts, by comparing the outcomes between the experimental group and the control group. The two primary outcomes include (1) the proportion of smokers who enroll in any SC service in Hong Kong within 1 month of the recruitment; and (2) the proportion of smokers who report quit attempts at 1 month follow-up. Secondary outcomes include (1) the above outcomes at 3-month follow-up; (2) self-reported use of NRT in past month at 1- and 3-month follow-up; (3) self-reported tobacco abstinence in past 7 days and 4 weeks at 3- and 6-month follow-up; (4) biochemically validated abstinence at 6-month follow-up; (5) perceived importance, difficulty and confidence to quit smoking (score 0-10); (6) progression towards smoking cessation as measured by Incremental Behavior Change toward Smoking cessation (IBC-S) [1]. All self-reported outcomes will be assessed either

by telephone or WhatsApp by allocation-blinded interviewers at 1, 3 and 6 months after the recruitment. Self-reported quitters (no use of tobacco products for 7 days) will be invited for examination of exhaled carbon monoxide with a Smokerlyzer, and to undertake a saliva cotinine test. Validated quitters were defined by exhaled CO < 4 ppm and salivary cotinine < 10 ng/ml, which have been confirmed as the cut-off in clinical trials to verify smoking abstinence [2,3]. A HK\$50 shopping voucher will be given for each participation of follow-up and biochemical validation. We have much experience for the above and have reported these in many papers [4-8].

6. Estimated duration and commencement date

Proposed starting date: 1 July 2018

Proposed study completion date: 30 June 2020

Expected final report date: 30 June 2020

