In the experimental sessions, the SCAs will approach and distribute souvenirs (e.g. a pen) or leaflets to the smokers at outdoor smoking hotspots for 3-4 hours. The souvenirs and leaflets will have SC messages, quitline number and other SC services. If a smoker is willing to accept them and talk to the SCAs, the SCAs will advise the smoker to quit using the AWARD protocol. The AWARD protocol includes (1) Ask the smoking history, (2) Warn about the high risk (i.e., half of the smokers will die of smoking-related diseases), (3) Advise to quit, (4) Refer to the SC clinics of TWGHs and (5) Repeat the above advice (Do-it-again) [4]. Our previous studies have shown that the AWARD protocol is a feasible and appropriate tool used by non-healthcare professionals to promote smoking cessation [4-6]. If the smoker is interested in using the SC services, the SCAs will introduce NRT to the smoker and conduct a preliminary assessment of his/her eligibility for enrolling in the "NRT sampling" programme. The SCAs will invite him/her to go to the smoking cessation

truck nearby to receive counselling by an onsite nurse. If the smoker is not eligible, he/she can still enroll in the cessation service provided by the SC clinics.

11. Intervention: NRT sampling and medication counselling

In the experimental sessions, an onsite nurse will assess whether each participant is fit for using NRT with further assessment on his/her current physical status, medication and blood pressure. If the participant is willing to use NRT to quit smoking and pass the nurse's assessment, he/she will be prescribed the NRT sample, regardless of whether they use NRT for smoking reduction and when the quit day is. The nurse will help the participant decide which type of NRT product (gum: 2mg, patch: 14mg or 21mg) that he/she can use and advise him/her on how to use the NRT based on his/her smoking habit and daily cigarette consumption. In addition, the nurse will deliver medication counselling which addresses five main components: (1) the benefits for using NRT in quitting, (2) withdrawal symptoms due to smoking cessation, (3) side effects of NRT, (4) instructions for using NRT, and (5) making appointments for TWGHs SC clinics. Afterwards, the participant will receive 1-week free NRT and an instruction card about the use of NRT.

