15.2.3 Participants who do not make an intake appointment

The participants will receive motivational messages from the research assistant around one week after baseline to encourage them to quit and enroll in one of the SC clinics.

16. Indicators and targets

Our targets will be as follows:

1. Train 40 tertiary students to be SCAs
2. Deliver brief SC advice to 2,400 smokers (1,200 in the experimental and 1,200 in the control group)

Experimental group

3. Provide NRT sample to 720 smokers (60% of all the approached smokers), who also consent to the follow-up
4. Motivate 288 smokers (40%) to use any SC services
5. Motivate 144 smokers (20%) to attempt quitting (intended abstinence for at least 24 hours).

Control group

6. 360 smokers (30% of all the approached smokers) will consent to the follow-up.
7. Motivate 72 smokers (20%) to use any SC services
8. Motivate 28 smokers (8%) smokers to attempt quitting

Both groups

9. 108 smokers report abstinence (for the past 7 days) at 6-month follow-up (30% of all

the 360 smokers who use any SC services)

17. Sample size determination

To detect a significant difference of the rate of quit attempt (20% versus 8%) with normal test and a power of 95% and 5% significance level, we need 485 subjects in the RCT (allocation ratio 2:1; 323 vs 162). Based on the method of Eldridge et al. (2006) [26], conservatively assuming that we could recruit 8 participants per session on average and the intra-cluster correlation coefficient was 0.1, the design effect is estimated to be 1.7. Thus, the minimum sample size required for the trial is 825 (=1.7 X 485) participants and 60 sessions in total. With the similar calculation, the required sample size for detecting a significant difference in the proportion of using any SC service is 421. Therefore, our targeted sample size is sufficient to answer the research question.

18. Data analyses

To assess the change of knowledge, attitude and practice of SC due to the participation of the SCA workshop, all the outcomes will be tested by McNemar's test (binary outcomes) and pair-sample t-test (continuous outcomes).

To assess the effect of NRT sampling to the recruitment outcomes, the number of smokers who accept the brief advice or consent for the trial in each promotion session will be the outcome variables of Poisson regression model, with group allocation as the predictor, and total number of approached smokers in that promotion session as the offset variable.

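### The recruitment model in Section 18 tests only the proportion limb of the primary process hypothesis, on a numerator that omits clinic-only recruits; the count limb has no specified test

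*Combined protocol and SAP*

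**What the plan says.** Section 5, Phase 2, states: "The primary process outcomes are the number and proportion of smokers that can be recruited for further follow-up", and it widens the definition of a recruit: "including those who will not participate in the RCT but agree to enroll in the SC clinics". The hypothesis has two limbs. Sessions offering the NRT sample "will recruit more smokers, and greater proportion of recruited smokers among those who will be approached". Two further indicators are listed as secondary process outcomes: "total number of smokers who can be approached in outdoor urban places" and "number of smokers who accept the brief SC advice".

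Section 18 gives one model for recruitment, a Poisson regression with group as predictor. In it, "the number of smokers who accept the brief advice or consent for the trial in each promotion session will be the outcome variables", and the model takes the "total number of approached smokers in that promotion session as the offset variable".

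Three other places bear on the point. Section 8 says that all recruitment outcomes will be compared between the groups, without naming a method. Section 10 shows that clinic-only recruits can exist: "If the smoker is not eligible, he/she can still enroll in the cessation service provided by the SC clinics". Section 13 says that recruitment staff know the allocation before each session.

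**The concern.** A Poisson model with log(number approached) as offset estimates recruits per smoker approached. That answers the proportion limb. It does not say whether a session with NRT samples yields more recruits, which is the other limb. The yield of a session depends on how many smokers are approached as well as on the share who agree. The number approached is observed after allocation and is one of the plan's own process outcomes, so any effect of the arm on it is removed from the group coefficient.

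The numerators also differ from the outcome. Advice acceptance is a secondary process outcome. Trial consent is only the RCT part of the primary one. Neither count includes a smoker who stays outside the trial but agrees to enrol in a clinic, although Section 5 counts that smoker as recruited.

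The stake is the Phase 2 conclusion. If Section 18 is followed as written, one of the two primary process outcomes has no analysis and the other is analysed on a narrower definition. The count limb is not incidental: Section 8 expects experimental sessions to recruit more smokers and uses that expectation to justify the 2:1 participant ratio.

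**Working it through.** **Outcome and model side by side**

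| | Section 5, Phase 2 | Section 18 |
|---|---|---|
| Quantities | Number and proportion recruited | Rate per smoker approached |
| Numerator | Trial participants plus clinic-only recruits | Advice acceptance; trial consent |
| Number approached | A secondary process outcome | The offset |

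**Inputs.** Section 16 plans 1,200 smokers per group, 720 recruited in the experimental group (60% of those approached) and 360 in the control group (30%). I take these as the trial-consent proportions. The plan gives no power or sample size for the process hypothesis, and no figure for clinic-only recruits.

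**Step 1: the plan's own figures.** 0.60 × 1,200 = 720 and 0.30 × 1,200 = 360, as stated. The ratio of proportions is (720/1,200) / (360/1,200) = 2.0, and the ratio of total counts is 720/360 = 2.0. The two agree because the planned denominators are equal.

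**Step 2: what the offset model estimates.** With log(approached) as offset,

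exp(group coefficient) = (recruited/approached, experimental) / (recruited/approached, control).

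The ratio of recruits per session is this quantity multiplied by r, the ratio of smokers approached per session, experimental to control. At 60% versus 30%:

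count ratio = (0.60 × r) / 0.30 = 2.0 × r.

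The documents give no per-session value of r, so the values below are assumptions.

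| r (assumed) | Offset model | Count ratio per session |
|---|---|---|
| 0.5 | 2.0 | 1.0 |
| 0.8 | 2.0 | 1.6 |
| 1.0 | 2.0 | 2.0 |
| 1.2 | 2.0 | 2.4 |
| 1.5 | 2.0 | 3.0 |

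The equal totals in Section 16 correspond to r = 1.0 only if both arms have the same number of sessions, which is also an assumption.

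**Step 3: the numerator.** Let e and c be the clinic-only recruits as shares of smokers approached, experimental and control. The proportion ratio on the Section 5 definition is (0.60 + e) / (0.30 + c). All shares below are assumed.

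| e | c | Ratio |
|---|---|---|
| 0% | 0% | 0.60/0.30 = 2.00 |
| 5% | 5% | 0.65/0.35 = 1.86 |
| 10% | 10% | 0.70/0.40 = 1.75 |
| 5% | 20% | 0.65/0.50 = 1.30 |
| 15% | 5% | 0.75/0.35 = 2.14 |

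The ratio stays at 2.0 only when e = 2c. It falls when e is below 2c and rises when e is above 2c.

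**The case against.** The best defence is that the offset is correct for what it does. The hypothesis has an explicit proportion limb, and a Poisson model with number approached as offset is a sound way to test it. The model covers trial consenters, who are part of the primary numerator. Section 8 promises to compare every recruitment outcome, Section 5 has the ambassadors record all the indicators, and the planned equal denominators make the two ratios coincide. All of this stands, but it does not close the gap. The Section 8 promise carries no method, equal denominators are a target rather than a design constraint, and clinic-only recruits remain outside every modelled count.

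A reader might infer two stronger things. The first is that the primary process hypothesis is never tested. That goes too far, because the proportion limb is tested, on a narrower numerator.

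The second is that the offset model overstates the gain because counselling and dispensing slow down the experimental sessions. The documents do not support this. Ambassadors do the approaching, while nurses counsel and dispense at the truck (Sections 10, 11 and 22). Section 11 gives control sessions the same procedures apart from the sample and the instruction card, and it allows the sample to be posted. The number approached could differ in either direction, and a rate ratio overstates nothing unless it is reported as a count ratio.

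**Conclusion.** The concern holds in limited form. The count limb of the primary process hypothesis has no specified test, and the proportion limb is modelled without clinic-only recruits. This is more than missing detail, since following Section 18 exactly answers a narrower question than Section 5 asks.

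The size cannot be fixed from the documents. For a 20% difference in number approached per session in either direction, the count ratio would lie between 1.6 and 2.4 while the model reports 2.0. Clinic-only shares of 5% to 10% in both arms would move the proportion ratio to between 1.86 and 1.75, and unequal shares could move it further, either way. These figures rest on the 60% and 30% targets and on assumed values for everything else. They show that the quantities can separate, not that they will.

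The consequence is confined to Phase 2. The two primary quitting outcomes have their own generalized estimating equations analysis. The change should be made, but it does not threaten the trial's main comparison.

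**What to change.** In Section 18, define a recruit as Section 5 does: trial consent plus clinic-only recruits. Fit two session-level models to that count, with group as predictor:

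1. For the number: recruits per session without the approached offset, with log(session length) as exposure if start and end times were recorded. If they were not, plain counts per session will do, since sessions are all planned at about 3–4 hours.
2. For the proportion: the same count with log(number approached) as offset.

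Use a variance robust to overdispersion in both. Sessions are the randomised clusters, and counts of smokers sharing a session are likely to vary more than a Poisson model allows. Keep advice acceptance as a secondary outcome and report number approached by arm, so that a reader can see how the two ratios relate.

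The cost is one more model, on indicators that Section 5 already has the ambassadors document. Session times are not among the listed indicators and would have to be added. The downside is precision: the count model does not absorb session-to-session variation in footfall, which the approached offset does. Sessions are allocated within hotspots (Section 12), so a hotspot term could be considered to recover some of it.

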In the control sessions, all the above procedures for the experimental group will be applied, except that they will not receive an NRT sample and an instruction card about the use of NRT. Instead, they will be advised to obtain free NRT by enrolling in the SC clinics. Both groups will receive a one-page leaflet provided by the SC clinics.

As this trial is a pragmatic trial, flexible procedures will be adopted based on the actual interaction with the participant. Firstly, the intervention components and filling in of baseline questionnaire may be carried out prior to seeking the consent from the participant if it is deemed more suitable in the situation and can make the procedures run more smoothly. Secondly, if the recruitment venue is not suitable for drug dispensing, the NRT sample and the use instructions will be register-mailed to the participants' address instead of given immediately. All NRT will be prescribed by registered nurses. The research assistant will also contact the participants to confirm that they have received the NRT. This arrangement of mailing the NRT sample complies with the Pharmacy and Poisons Ordinance of the Drug Office.

12. Randomization

We will use cluster randomization based on promotion session as the cluster unit because the procedures of individual randomization are difficult in outdoor areas as found in our pilot RCT. The PI will randomly allocate the promotion sessions within a hotspot to the 2 groups by a list of group allocation which is based on a list of random numbers from Excel programme. Each hotspot will have 2 or more promotion sessions, and each session will last for about 3-4 hours. If a hotspot has 2 promotion sessions on 1 single day, the 2 sessions will be allocated into the same RCT group, and we will organize 2 more promotion sessions in this hotspot on another day.

13. Allocation concealment

All recruitment staff will know the group allocation before each promotion session, so no group concealment can be done.

14. Blinding

Participants cannot and will not be blinded to the intervention. Assessors of the follow-up outcomes and the research analysts will not be involved in the recruitment and intervention delivery, and will be blinded to the group allocation (single blindness).

15. Follow-up

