15.1 Intervention Group

15.1.1 Participants who receive NRT samples and whose quit day is within one week after baseline

A TWGHs nurse who is experienced in delivering smoking cessation will contact the participants around one week after baseline. The nurse will provide more intensive counseling to the smoker, especially on the use of NRT. All the smokers will be asked if

they have used any NRT and have any difficulties in using NRT, and will be given more counseling via telephone if necessary.

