To compare the two primary quitting outcomes (binary) between experimental and control group, generalized estimating equations model will be used. Other secondary outcomes will be analyzed with either generalized estimating equations models (binary outcomes; e.g. tobacco abstinence) or linear mixed model (continuous outcomes; e.g. perceived importance to quit smoking).

Cost analysis will be conducted to assess if the intervention is cost-effective, as what we did in our published paper [5]. Direct operating costs included salary (of training personnel, research assistants and SCAs), recruitment, telephone follow-up and publicity items. The total operation costs for the experimental group will include the cost for NRT sampling. Costs for study design, venues for training (provided by HKU), analysis, report writing and

irrelevant administration were excluded. In each group, the cost per successfully recruiting a smoker to receive any SC service was calculated by dividing the total cost by the number of smokers who report use of any smoking cessation. Similarly, the costs per quit attempt will also be calculated.

19. Time-line:

	2018						2019												2020						
	7	8	9	10	11	12	1	2	3	4	5	6	7	8	9	10	11	12	1	2	3	4	5	6	
HCPS – NRT sampling																									
Development of the intervention, instruments and protocol																									
Site selection																									
Recruitment of ambassadors																									
Training for staff, ambassadors and nurses																									
Subject recruitments																									
3-day / 1-month follow-up																									
3-month follow-up																									
6-month follow-up (+validation)																									
6-month follow-up for SCAs																									
Data entry and cleaning																									
Data analysis																									
Report preparation																									

20. Describe any unusual or discomforting procedures to be used: Nil.

21. Are there any hazards associated with the investigation? No.

22. Ethical and legal issues

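### The cost analysis plans only each arm's average cost per outcome, which does not estimate what an additional service user or quit attempt costs, and it does not say where nurse time is counted.

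*Combined protocol and SAP*

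**What the plan says.** Section 18 (Data analyses) gives the purpose: "Cost analysis will be conducted to assess if the intervention is cost-effective". For each group, the cost of bringing one smoker into a cessation service is found by "dividing the total cost by the number of smokers who report use of any smoking cessation". Then: "Similarly, the costs per quit attempt will also be calculated". The section plans no difference in cost, no ratio of differences, no interval and no threshold.

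On cost items, Section 18 states: "Direct operating costs included salary (of training personnel, research assistants and SCAs), recruitment, telephone follow-up and publicity items". It adds: "The total operation costs for the experimental group will include the cost for NRT sampling". Study design, training venues, analysis, report writing and unrelated administration are excluded. Nurses appear neither among the listed salaries nor among the exclusions.

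Nurses nevertheless do much of the work. Under Section 11, "an onsite nurse will assess whether each participant is fit for using NRT with further assessment", and the nurse then helps choose a product and gives medication counselling. For control sessions the same section says "all the above procedures for the experimental group will be applied, except that they will not receive an NRT sample" or the instruction card. For sample recipients with an early quit day, Section 15.1.1 says: "A TWGHs nurse who is experienced in delivering smoking cessation will contact the participants around one week after baseline".

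**The concern.** Whether sampling is cost-effective is a question about what it adds: how much more is spent, and how many more smokers use a service or try to quit. Control participants receive almost everything except the sample, and Section 16 expects 72 service users and 28 quit attempts among them. The experimental arm's average mixes the added cost and added outcomes with the cost and outcomes the two arms share. It therefore moves with the shared cost even when the price of an extra outcome does not.

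Nurse time is the second gap. The experimental arm should recruit twice as many participants (720 vs 360), and sample recipients get more intensive nurse follow-up. If this labour is not counted, the cost difference between the arms is understated. What is at stake is the economic conclusion only.

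**Working it through.** **Inputs from Section 16.** 1,200 smokers advised per arm; 60% and 30% join follow-up; 40% and 20% of those use a service; 20% and 8% attempt to quit.

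**Reproducing the targets.**
- Participants: 1,200 × 0.60 = 720; 1,200 × 0.30 = 360.
- Service users: 720 × 0.40 = 288; 360 × 0.20 = 72. Difference 216.
- Quit attempts: 720 × 0.20 = 144; 360 × 0.08 = 28.8 (stated as 28). Difference 116, using 28.

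**Formulas.** With total cost C and outcome count n in arms E and C, the planned measure is C_E / n_E. The incremental measure is (C_E − C_C) / (n_E − n_C), on equal numbers approached.

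**Illustration.** The documents give no cost totals, so C_C = 100 and C_E = 200 are assumed.
- Per user: 200 / 288 = 0.69; incremental 100 / 216 = 0.46. The average is 50% higher.
- Per quit attempt: 200 / 144 = 1.39; incremental 100 / 116 = 0.86. The average is 61% higher.

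**When the direction changes.** The average exceeds the incremental cost exactly when C_E / C_C < n_E / n_C. The crossover is 288 / 72 = 4.0 for users and 144 / 28 = 5.1 for quit attempts.

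**Using the protocol's NRT price.** Section 7 quotes US$5.43 per day. Suppose the arms differ only by one week of NRT for 720 recipients: 5.43 × 7 × 720 = US$27,367. Then an extra user costs 27,367 / 216 = US$127 and an extra quit attempt 27,367 / 116 = US$236, whatever the shared cost. The planned averages depend heavily on the assumed shared cost:

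| Assumed shared cost per arm | Average per user, E vs C | Average per quit attempt, E vs C |
|---|---|---|
| US$20,000 | 164 vs 278 | 329 vs 714 |
| US$50,000 | 269 vs 694 | 537 vs 1,786 |
| US$100,000 | 442 vs 1,389 | 884 vs 3,571 |

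**Why the base matters.** Per smoker approached, 200 vs 100 is a cost difference of 100 / 1,200 = 0.083 and a difference in users of 0.24 − 0.06 = 0.18, which returns 0.46. Per consenting participant, the costs are 200 / 720 = 0.28 and 100 / 360 = 0.28. The difference is zero and the extra users would appear free. Recruitment is itself expected to respond to sampling (Section 8), so participants are not a neutral base.

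**Nurse time.** Assume 15 to 60 minutes per participant at US$15 to 40 per hour in both arms (neither figure is in the documents), or US$3.75 to 40 each. The 360 extra experimental participants add US$1,350 to 14,400. The incremental cost rises from US$127 to between US$133 and 193 per extra user, and from US$236 to between US$248 and 360 per extra quit attempt. Heavier follow-up of sample recipients would add to this.

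**The case against.** **The incremental cost can be had by subtraction.** A reader might infer that the analysis is incapable of showing it. That goes too far: arm totals and outcome counts will exist, and with equal numbers approached the ratio follows directly. What stands is that the plan neither names this result nor fixes its base, and gives it no interval.

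**The averages need not flatter sampling.** A reader might infer that crediting the experimental arm with outcomes that would have occurred anyway makes it look cheap. At the plan's targets the reverse is likelier. With NRT as the only difference, a cost ratio above 4 would need a control total below 27,367 / 3 = about US$9,100. The ranking of the two averages is also sound in one sense: the experimental average is below control's exactly when the incremental cost is below control's average. That still does not tell a funder what an extra outcome costs.

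**Nurse time may already be counted.** A reader might infer that it is left out and that the experimental arm is thereby favoured. The documents do not establish this. Recruitment, telephone follow-up or NRT sampling could each cover part of it. On-site counselling also occurs in control sessions, and nurses contact control participants with intake appointments (Sections 15.2.1 and 15.2.2). For sample recipients with a later quit day, a research assistant makes the one-week contact and the nurse follows after the quit day (Section 15.1.2). With equal minutes per participant, adding nurse time raises the experimental average by US$9 to 100 per user and control's by US$19 to 200, so omission would not favour the experimental arm in that comparison. It would understate the incremental cost.

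**Section 18 defers to an earlier published trial (reference 5) for the method.** That paper is not available here and may contain an incremental step. The protocol describes none.

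**Cost is not a listed objective or outcome** (Sections 4 and 5). This limits the weight of the point but does not remove it, because Section 18 promises a cost-effectiveness judgement.

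**Conclusion.** The point holds as a mismatch between the stated purpose and the planned measure. Arm averages do not estimate the cost of an additional service user or quit attempt. At the plan's targets and assumed costs of 200 vs 100, they exceed it by 50% and 61%. They overstate it at any cost ratio below 4.0 (users) or 5.1 (quit attempts) and understate it above. The outcome counts are the plan's targets. The cost totals are assumed, and the quoted NRT price may not be what the project pays, so the sizes are illustrative; the algebra is not.

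On nurse time, the supportable conclusion is that the plan does not say where it is counted, and that it differs between arms through recruitment numbers and follow-up. The documents support neither a claim that it is omitted nor a claim that the planned averages favour sampling. No primary or secondary trial comparison is affected.

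**What to change.** In Section 18:

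- Make the main cost result the difference in cost divided by the difference in outcomes, once for service use and once for quit attempts. Compute it per smoker approached or per session, not per consenting participant.
- Give an interval that respects the session as the unit of randomisation, for example by resampling sessions, where costs can be assigned to sessions. If they cannot, say so and show a range over stated cost assumptions.
- Count nurse time in both arms, on site and in follow-up. Where hours were not recorded, estimate them with stated assumptions and a range.
- State whether the cost of running the truck is included.
- Keep the arm averages as description.

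The arm totals and counts already planned supply the point estimate. The price is a modest extra analysis, some work to apportion costs to sessions, and a nurse-time estimate. The protocol is dated at its own planned completion date, so that estimate may have to be reconstructed from records.
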